1.2 Secondary Objectives

Secondary Objective A: *To determine the effect of active, inhibitory rTMS (cTBS) over L-DLPFC on modulating the neural network that underlies hypnotic intensity.*

Secondary Hypothesis A: *Active, inhibitory rTMS (cTBS) over L-DLPFC will modulate the neural network that underlies hypnotic intensity by decreasing activity in L-DLPFC and dACC as compared to sham rTMS (sham cTBS) as measured by BOLD fMRI and interleaved TMS-MRI.*

Secondary Objective B: *To determine the effect of active, inhibitory rTMS (cTBS) over L-DLPFC on enhancing hypnotizability (as measured by the Hypnotic Induction Profile-HIP and Stroop Task) and hypnotic intensity (as measured by the Hypnotic Intensity Scale-HIS).*

Secondary Hypothesis B: *Active, inhibitory rTMS (cTBS) over L-DLPFC will increase the HIP and HIS scores as well as hypnotic reduction of the Stroop Effect as compared to sham rTMS (sham cTBS).*

Secondary Objective C: *To determine the effect of active, inhibitory rTMS (cTBS) over L-DLPFC on the neural network underlying the conflict regulation system as a surrogate of effective modulation of the neural circuitry that underlies hypnotizability.*

Secondary Hypothesis C: *Active, inhibitory rTMS (cTBS) over L-DLPFC will modulate the neural network that underlies conflict regulation by producing greater increases in functional connectivity between the right inferior frontal gyrus (rIFG) and the default mode network (DMN) as compared to sham rTMS (sham cTBS).*

Secondary Objective D: *To determine the effect of active, inhibitory rTMS (cTBS) over L-DLPFC on the neural network that underlies the post-hypnotic Stroop Effect.*

Secondary Hypothesis D: *Post-hypnotic instruction of word blindness after active, inhibitory rTMS (cTBS) over L-DLPFC will reduce dACC activity during the Stroop task (similar to high hypnotizables) as compared to sham rTMS (sham cTBS).*

Secondary Objective E: *To determine the effect of active, inhibitory rTMS (cTBS) over L-DLPFC on modulating the neural network that underlies hypnotic analgesia (HA).*

Secondary Hypothesis E: *Active, inhibitory rTMS (cTBS) over L-DLPFC will modulate the neural network that underlies HA by producing a decrease in activity and an increase functional connectivity among the anterior cingulate, dorsolateral, insular, and somatosensory cortices (hypnotic analgesia network) as compared to sham rTMS (sham cTBS).*

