- Spectroscopy: Non-invasive magnetic resonance spectroscopy (MRS) will be used to quantitatively measure brain metabolites, including both inhibitory and excitatory neurotransmitters as well as markers of inflammation.

Pre-rTMS Stroop Assessment

Hypnotic Stroop and Non-Hypnotic Stroop Pre-rTMS Scan Session: This session includes all of the pre-rTMS questionnaires, behavioral evaluations and scans necessary to compare to the post-rTMS.

- Medication Washout, Drug Screen, Pregnancy Test Form: This form will be administered at the beginning of each pre-rTMS assessment to ensure medication washout compliancy (if applicable), document drug screen results, and screen for pregnancy (if applicable).
- Hypnotic Induction Profile: This administration of the HIP will serve as the baseline measure for comparison after the rTMS stimulation session(87). HIP will be measured on three separate occasions throughout the stroop assessment visit - 1) immediately following the pre-rTMS stroop MRI session, 2) immediately following rTMS, and, 3) immediately following the post-rTMS stroop MRI session.
- Stroop Task: This administration of the Stroop task will serve as the baseline measure for comparison to the post-rTMS session(32, 118).
- Pre-TMS Hypnotizability Scan Session (1 hour duration)
 - Structural Acquisition (T1): This structural scan is necessary for several reasons: demonstration that the participant's brain is structurally normal, imaging analysis, and rTMS targeting(81).
 - BOLD fMRI Acquisitions
 - Resting State: This is the baseline scan required for the primary endpoint. Individuals with high hypnotizability have been demonstrated to have higher functional connectivity between the dorsolateral prefrontal cortex and the dorsal anterior cingulate cortex (31).
 - Stroop Task: Brain activity while performing conflict tasks has been demonstrated to be different depending on a subject's level of hypnotizability. This baseline would demonstrate the subject's normal functional brain response to the Stroop Task

(32). Functional brain response to the stroop task will be measured following hypnosis (Hypnotic Stroop) and non-hypnosis (Non-Hypnotic Stroop) audio instructions. These acquisitions will be randomized to prevent order effects. Highly hypnotizable individuals can have a loss of the Stroop Effect with specific post-hypnotic instruction (119, 120) which correlates with the reduction in neural activity during conflict (35).

Pre-rTMS Analgesia Assessment

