9.6 Outcomes

9.6.1 Primary Outcomes

Primary Mechanistic Outcome Measure: *To determine the effect of active, inhibitory rTMS (cTBS) over L-DLPFC on modulating the connectivity of the neural network that underlies hypnotizability.*

This study will test an augmentation approach where one modality (rTMS) (30) is being used to modulate the neural circuitry underlying another technique (hypnotizability) in an effort that this combinatory approach may transiently produce the high hypnotizable phenotype on formal testing(31). It will be determined if modulation of the neural circuitry that underlies hypnotizability with rTMS can potentially produce a brain connectivity pattern that resembles a highly hypnotizable individual(31). This study proposes to measure the change in hypnotizability by contrasting the functional connectivity between the L-DLPFC and dACC at pre- and post-rTMS for both rTMS conditions (active versus sham cTBS) (31).

Hypnotizability Scans for Primary Outcome Measure: All participants will receive the same identical pre-rTMS resting state scan(31, 51). After randomization (to either active DLPFC rTMS or sham rTMS) where one half (n=45) will receive active DLPFC rTMS (cTBS), and one-half sham DLPFC rTMS (cTBS) (n=45)(30), all participants have their hypnotizability post-rTMS scan session(31, 51).

fMRI Preprocessing and Analysis: All fMRI data will be preprocessed and analyzed using FSL (FMRIB Software Library, version 5.0) (88). Physiological signals will first be removed using RETROICOR and RVHRCOR (97, 98). The first 6 volumes will be discarded to allow for signal stabilization. The following standard preprocessing steps will then be applied: motion correction using least square minimization (99), removal of non-brain tissues (100), resampling to 2 x 2 x 2 mm³ voxels, spatial smoothing with a 6 mm full-width at half-maximum (FWHM) Gaussian kernel to improve functional alignment between participants, and mean-based intensity normalization of all volumes by the same factor and high pass temporal filtering with a Gaussian-weighted least-squares straight line fitting, and linear registration using the FMRIB's Linear Registration Tool (FLIRT, 6 degrees of freedom (DOF)) to T1-weighted anatomical images and Montreal Neurological Institute (MNI) standard space.

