9.6.2 Secondary Outcomes

Secondary Outcome Measure A: *To determine the effect of active, inhibitory rTMS (cTBS) over L-DLPFC on modulating the activity and connectivity of the neural network that underlies the hypnotic state.*

This study is designed to measure the change in hypnotic intensity by contrasting the BOLD activity(133), TMS-BOLD activity(130), and functional connectivity(133) between the L-DLPFC and dACC at pre- and post-rTMS time-points for both rTMS conditions (active L-DLPFC rTMS (cTBS) and sham L-DLPFC rTMS (cTBS))(31).

Hypnosis Scans for Secondary Outcome Measure A: All participants will receive the same identical pre-rTMS resting state scan(31, 51). After randomization (to either active DLPFC rTMS or sham rTMS) where one half (n=45) will receive active DLPFC rTMS (spaced cTBS), and one-half sham DLPFC rTMS (spaced cTBS) (n=45)(30), all participants have their hypnotizability post-rTMS scan session(31, 51).

fMRI Preprocessing and Analysis: All fMRI data will be preprocessed and analyzed using FSL (FMRIB Software Library, version 5.0) (88) and in the manner described in the Primary Outcome. For group analysis, FMRIB's local analysis of mixed effects will be used within a mask of our a priori ROIs ACC and DLPFC, thresholded using family-wise error (FWE) corrected $Z > 2.3$; cluster $p < 0.05$. Average contrast of parameter estimate values will be extracted from our ROIs and Spearman's correlations will be calculated between these values and differences in active versus sham rTMS.

Secondary Hypothesis A: *Active, inhibitory rTMS (cTBS) over L-DLPFC will modulate the neural network that underlies hypnosis by producing greater increases in activity and functional connectivity between L-DLPFC and dACC.*

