Connectivity between L-DLPFC and dACC will be assessed with resting state functional connectivity MRI(31, 51) at the baseline time-point and as well as at the post-rTMS time-point for both rTMS conditions (active and sham cTBS). Analyses will be restricted to the dACC and L-DLPFC for this Secondary Outcome Measure. To determine if rTMS condition during the hypnotic state is specifically associated with change in dACC and DLPFC activity and functional connectivity, a mask restricted to dACC and DLPFC will be utilized to extract the fMRI activity and connectivity data. It is expected that the correlation in active rTMS group over L-DLPFC to be stronger than the correlation obtained in the sham rTMS group. Regression analysis will determine the strength of the relationship between the reductions of fMRI activity between dACC and L-DLPFC during the active versus sham rTMS conditions. Regression analysis will be used to investigate whether greater connectivity will be present between L-DLPFC and dACC for active rTMS versus sham rTMS.

Secondary Outcome Measure B: *To determine the effect of active, inhibitory rTMS (cTBS) over L-DLPFC on enhancing hypnotizability (as measured by the Hypnotic Induction Profile-HIP and Stroop Task) and hypnotic intensity (as measured by the Hypnotic Intensity Scale-HIS).*

Augmenting hypnosis with active rTMS may potentially produce an intervention that works better (i.e. deeper hypnotic state) and/or extends to a larger part of the population (makes more of the population hypnotizable)(26).

Hypnosis Related Measures: All participants will receive a baseline Stroop task, HIP, and HIS. After randomization (to either active DLPFC rTMS or sham rTMS) where one half (n=45) will receive active rTMS (cTBS), and one-half sham rTMS (cTBS) (n=45)(30), participant will be placed back in scanner and their HIS will be reassessed. After the post-rTMS scans, all participants will be reassessed with the Stroop task and the HIP.

Analysis of Measures: Changes in HIP, Stroop Effect, and HIS between active DLPFC rTMS and sham rTMS conditions will be compared using ANOVA. It is expected that there will be a significantly greater mean increase in HIP, HIS, and Stroop Effect with active rTMS condition than with the sham rTMS condition at the $p < 0.05$, level.

Secondary Hypothesis B: *Active, inhibitory rTMS over DLPFC will increase hypnotizability and hypnotic intensity as compared to sham rTMS.*

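### Secondary Outcome A repeats the primary's resting-state connectivity test, ties its activity part to no hypnosis run, and lists TMS-BOLD without a stated acquisition or model

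*Combined protocol and SAP*

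**What the plan says.** Section 9.6.2 of the combined protocol and SAP sets Outcome A the task of finding the effect of stimulation on "modulating the activity and connectivity of the neural network that underlies the hypnotic state". Sections 1.2, 3 and 9.1 word the same objective in terms of hypnotic intensity. The measures are to come from "contrasting the BOLD activity(133), TMS-BOLD activity(130), and functional connectivity(133) between the L-DLPFC and dACC at pre- and post-rTMS time-points". Section 1.2 likewise has the hypothesis tested "as measured by BOLD fMRI and interleaved TMS-MRI".

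The scans assigned to A are introduced thus: "Hypnosis Scans for Secondary Outcome Measure A: All participants will receive the same identical pre-rTMS resting state scan". After randomisation, participants have the post-rTMS hypnotizability session. For the analysis, section 9.6.2 says "Connectivity between L-DLPFC and dACC will be assessed with resting state functional connectivity MRI", at baseline and after stimulation, in both arms.

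Separately, section 6.2.2 describes runs acquired under hypnosis on the Stroop day: "Functional brain response to the stroop task will be measured following hypnosis (Hypnotic Stroop) and non-hypnosis (Non-Hypnotic Stroop) audio instructions". Sections 6.2.2 and 6.2.5 give matching hypnosis and non-hypnosis runs for the pain task, and both pairs are acquired before and after stimulation.

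**The concern.** The protocol itself separates rest from hypnosis. Section 2.2 treats resting L-DLPFC–dACC connectivity as a marker of the trait, hypnotizability. It describes different findings during hypnosis: lower dACC activity and altered L-DLPFC connectivity with the insula and posterior cingulate. Section 9.1, under Secondary Objective A, says that activity and connectivity measures differ between the hypnotic state and waking rest. A resting scan is therefore the wrong source for an outcome about the hypnotic state.

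Two things are at stake. A positive primary result would reappear under a hypnotic-state label and could be read as corroboration. And the state question that A poses would go unanswered by A, although scans bearing on it are planned.

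**Working it through.** The plan gives no figure for Outcome A. Section 9.2 sets no power target for it, so there is nothing to reproduce. The check is a comparison of texts.

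**Step 1: the connectivity part.**

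| Element | Primary (9.6.1) | Outcome A (9.6.2) |
|---|---|---|
| Pre-stimulation scan | Resting state | Resting state, same sentence |
| Post-stimulation scan | Hypnotizability session | Hypnotizability session |
| Connectivity method | Resting-state fcMRI | Resting-state fcMRI |
| Region restriction | dACC and L-DLPFC | dACC and L-DLPFC |
| Processing | FSL pipeline described there | By reference to the primary |
| Comparison | Regression, active versus sham | Regression, active versus sham |

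The scan entries differ only in their label. The primary's reads "Hypnotizability Scans for Primary Outcome Measure: All participants will receive the same identical pre-rTMS resting state scan". One small difference exists: A's group-level mask is worded as ACC and DLPFC, but its restriction sentence returns to dACC and L-DLPFC.

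Write C for a participant's post-minus-pre change in resting L-DLPFC–dACC connectivity. Section 9.2 models a change outcome as Y = α + γZ + ε, with Z the randomised arm. If Y = C for both the primary and A, the estimate of γ and its p-value are the same number.

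The consequence for error rates is simple. At the planned 0.05 level under the null, two independent tests would both be falsely positive with probability 0.05 × 0.05 = 0.0025. When the second test is the first repeated, that probability is 0.05. The second result adds no information.

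**Step 2: the activity part.** Section 9.7 identifies Secondary Hypothesis A with the effect on L-DLPFC and dACC activity. Section 9.6.2 refers to the hypnotic state when it describes the mask, but names no run acquired under hypnosis and no contrast with non-hypnosis. Section 9.6.1 puts activity in the same two regions into the primary hypothesis, measured by fALFF. If A's activity is taken from the resting scans assigned to it, it overlaps that measure. Outcomes C, D and E, by contrast, each name a task or pain scan.

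**Step 3: TMS-BOLD.** It is named in sections 1.2, 3, 9.1 and 9.6.2. The scan lists in 6.2.2 and 6.2.5 contain no interleaved run, and the stimulation procedure in 6.2.4 has none. The schedule in 6.1 does not list individual MRI sequences, so its silence carries little weight alone. Section 5.1 places cTBS outside the scanner, which does not by itself rule out a separate probe. The analysis text for A contains no TMS-BOLD model.

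**Step 4: what is available.** Section 3 says that hypnosis is induced in the scanner. Two days, each with a pre- and a post-stimulation session, give 2 × 2 = 4 sessions per participant, each with a hypnosis and a non-hypnosis acquisition. The Précis also promises a between-group comparison of activation during the induction, but no induction-only run is listed.

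The text of A needs rewriting in any case. Sections 1.2 and 9.1 predict decreased activity and section 9.6.2 predicts increased activity. Section 3 adds insula and posterior cingulate connectivity, which the region restriction in 9.6.2 excludes.

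**The case against.** The strongest defence is that A is chiefly an activity outcome. Section 9.7 says so, and sections 9.1 and 9.2 give the connectivity portion of the grant's Hypothesis 1a to the primary. The connectivity sentences in 9.6.2 would then be secondary text. This stands, and it confines the exact duplication to the connectivity part. It does not supply the missing hypnosis run for activity.

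A reader might infer that A cannot answer its question at all. The documents do not support that. The post-rTMS hypnotizability session in 6.2.5 includes hypnosis Stroop runs as well as rest, and 9.6.2 states an intent to look at the hypnotic state. The run assignment could be completed. Yet A names only a resting scan before stimulation, and a pre-to-post change needs the same kind of run at both times.

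A reader might also infer that A as a whole is perfectly correlated with the primary. That would hold only for the connectivity component, and only if the same scan day or days feed both. The documents do not say which day feeds A.

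Nor do the documents show that TMS-BOLD was never acquired. The Précis promises an unspecified perturbation technique on the analgesia day, and the stimulation manual and figures are not in the available text. What can be said is that no acquisition is specified there.

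Finally, hypnosis would not go wholly untested. Outcome D uses post-hypnotic-suggestion Stroop scans and Outcome E uses hypnotic-analgesia scans, both including L-DLPFC and dACC. Sections 9.2 and 9.7 also put more emphasis on effect sizes than on significance for A. That lowers the stakes, but a repeated effect size is still the same evidence.

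**Conclusion.** The point holds in a limited form. As specified, A's connectivity test is the primary test under another label and does not measure the hypnotic state. Its activity part has no hypnosis-condition run assigned and overlaps the primary's resting activity measure. Its TMS-BOLD component has no specified run or model. The conclusion on duplication assumes that the same scan days are used for both outcomes and that the two mask descriptions mean the same regions. The primary analysis is unaffected. The matter should be corrected before A is reported, because otherwise one finding may be counted twice.

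**What to change.** - Remove the resting-state connectivity test from A, or state that it is the primary result and not separate evidence on hypnosis.
- Define A per participant as D = (H_post − N_post) − (H_pre − N_pre), where H and N are L-DLPFC and dACC activity (and, if kept, their connectivity) in the hypnosis and non-hypnosis runs. Compare arms with the section 9.2 model. Name the scan day or days. The in-scanner induction period promised in the Précis is an alternative source if it was recorded.
- State that the contrast is conditioned on the Stroop or pain task and its suggestion, so it does not isolate hypnosis, and that it overlaps Outcomes D and E.
- Give one direction for Hypothesis A throughout.
- Specify an acquisition and model for TMS-BOLD, or drop it.

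No new scanning is needed for the main contrast. The costs are some extra analysis and a secondary outcome that is task-conditioned and partly overlaps others. The stand-alone SAP of January 2024 does not mention A and describes data collection in the past tense. The redefinition should therefore be dated and labelled as made after data collection.

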6.2.5 Post-rTMS (Active and Sham) Evaluations

Post-rTMS Stroop Assessment

Hypnotic Stroop and Non-Hypnotic Stroop Pre-rTMS Scan Session: This session includes all of the post-rTMS behavioral evaluations and scans necessary to compare to the pre-rTMS.

- Hypnotic Induction Profile: This administration of the HIP will serve as the post-rTMS measure for comparison to the pre-rTMS stimulation session.
- Post-TMS Hypnotizability Scan Session (1 hour duration)
 - Structural Acquisition (T1): This structural scan is necessary for several reasons: demonstration that the participant's brain is structurally normal, imaging analysis, and rTMS targeting(81).
 - BOLD fMRI Acquisitions
 - Resting State: This is the scan required for evaluation of the primary endpoint. Individuals with high hypnotizability have been demonstrated to have higher functional connectivity between the dorsolateral prefrontal cortex and the dorsal anterior cingulate cortex (31).
 - Stroop Task: Brain activity while performing conflict tasks has been demonstrated to be different depending on a subject's level of hypnotizability. These scans will demonstrate the subject's functional brain response to the Stroop Task post-rTMS. Functional brain response to the stroop task will be measured following hypnosis (Hypnotic Stroop) and non-hypnosis (Non-Hypnotic Stroop) audio instructions. Randomization of hypnosis and non-hypnosis scan order for each participant will be kept consistent between both pre- and post-rTMS scans. Highly hypnotizable individuals can have a loss of the Stroop Effect with specific post-hypnoitic instruction (119, 120) which correlates with the reduction in neural activity

during conflict (35).

Post-rTMS Analgesia Assessment

Post-rTMS Analgesia Session: This hour-long scan session includes all of the post-rTMS behavioral evaluations and scans necessary to compare to the pre-rTMS.

- Hypnotic Induction Profile: This administration of the HIP will serve as the baseline measure for comparison after the rTMS stimulation session(87).
- Pre-TMS Scans
 - Structural Acquisition (T1): This structural scan is necessary for several reasons: demonstration that the participant's brain is structurally normal, imaging analysis, and rTMS targeting (81).
 - BOLD fMRI Acquisitions

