Hypnosis Scans for Secondary Outcome Measure D: All participants will receive the same identical pre-rTMS post-hypnotic suggestion Stroop task scan(35). After randomization (to either active DLPFC rTMS or sham rTMS) where one half (n=45) will receive active DLPFC rTMS (cTBS), and one-half sham DLPFC rTMS (cTBS) (n=45)(30), all participants have their post-rTMS post-hypnotic suggestion Stroop task scan session(35).

fMRI Preprocessing and Analysis: All fMRI data will be preprocessed and analyzed using FSL (FMRIB Software Library, version 5.0) and in the manner described in the Primary Outcome Measure. For group analysis, FMRIB's local analysis of mixed effects will be used within a mask of our a priori ROIs ACC and DLPFC, thresholded using family-wise error (FWE) corrected $Z > 2.3$; cluster $p < 0.05$. Average contrast of parameter estimate values will be extracted from the ROIs and Spearman's correlations will be calculated between these values and differences in active versus sham rTMS.

Secondary Hypothesis D: Post-hypnotic instruction of word blindness after active, inhibitory rTMS (cTBS) over L-DLPFC will reduce dACC activity during the Stroop task (similar to high hypnotizables) as compared to sham rTMS (sham cTBS).

Activity in dACC will be assessed with fMRI(35) at the baseline time-point and as well as at the post-rTMS time-point for both rTMS conditions (active and sham). Long-lasting (~1 hour) inhibitory rTMS (spaced continuous theta-burst stimulation approach(30)) will be applied to L-DLPFC and expect that the stimulation-induced functional connectivity between these two nodes would be increased as a surrogate of increased hypnotizability and therefore increased post-hypnotic Stroop Effect.

Analyses will be restricted to the dACC and DLPFC for this Secondary Outcome Measure. To determine if rTMS condition during the hypnotic state is specifically associated with change in dACC and DLPFC activity, a mask restricted to dACC and DLPFC will be utilized to extract the fMRI activity. The correlation in active rTMS group over L-DLPFC is expected to be stronger than the correlation obtained in the sham rTMS group. Regression analysis will determine the strength of the relationship between the reductions of fMRI activity between dACC and L-DLPFC with active versus sham rTMS conditions.

Secondary Outcome E: *To determine the effect of active, inhibitory rTMS over DLPFC on modulating the neural network that underlies hypnotic analgesia.*

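### Secondary Outcome B compares change in the Stroop Effect with no hypnotic contrast and with conflicting directions, so it cannot separate hypnotizability from a direct rTMS effect on conflict control

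*Combined protocol and SAP*

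**What the plan says.** All references are to the combined protocol unless stated.

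- **Hypothesis B, Section 1.2.** Hypnotizability is to be measured by the HIP and the Stroop task. Active rTMS is predicted to increase, besides the HIP and HIS scores, the "hypnotic reduction of the Stroop Effect as compared to sham rTMS (sham cTBS").
- **Hypothesis B, Sections 3 and 9.1.** The same hypothesis is repeated, but what increases is now the Stroop Effect itself.
- **Baseline, Section 6.2.2.** A Stroop test is listed outside the scan block: "This administration of the Stroop task will serve as the baseline measure for comparison to the post-rTMS session". The in-scanner Stroop is listed separately, under hypnosis and non-hypnosis instructions.
- **Post-rTMS list, Section 6.2.5.** It states: "This session includes all of the post-rTMS behavioral evaluations and scans necessary to compare to the pre-rTMS". Outside the scan block only the HIP appears. The Stroop task appears inside the one-hour scan: "Functional brain response to the stroop task will be measured following hypnosis (Hypnotic Stroop) and non-hypnosis (Non-Hypnotic Stroop) audio instructions". The order of the two conditions is kept the same before and after rTMS. The stated purpose is imaging: "These scans will demonstrate the subject's functional brain response to the Stroop Task post-rTMS".
- **Analysis, Section 9.6.2, Outcome Measure B.** "After the post-rTMS scans, all participants will be reassessed with the Stroop task and the HIP". Changes in HIP, Stroop Effect and HIS are compared between arms by ANOVA, and a larger mean increase in each is expected with active rTMS.
- **Table 2, Section 6.1.** One Stroop mark on the Stroop scan day, with no split into before and after.
- **SAP.** It describes the HIP analysis and the test of the blind. It does not mention the Stroop task.

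**The concern.** The rationale for using Stroop as a marker of hypnotizability rests largely on suggestion. Sections 6.2.2, 9.1 and 9.6.2 all say that highly hypnotizable people lose the Stroop effect after a specific post-hypnotic instruction. A measure built on that rationale needs a hypnotic condition and a non-hypnotic condition to compare it with. The comparison in Section 9.6.2 B names neither.

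This goes beyond missing detail, because Section 9.1, in support of the same outcome, says rTMS can shift the Stroop effect in both directions depending on frequency. The intervention therefore has a route to the outcome that does not pass through hypnotizability. A positive result could come from that route alone, and a null result could hide a real change in hypnotic responding. In addition, the direction in Section 9.6.2 would count a larger Stroop Effect as success, whereas Section 1.2 expects hypnosis to reduce it more.

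**Working it through.** The plan gives no sample size, power or effect size for the Stroop comparison, so there is no figure to reproduce. The check is a comparison of sections, followed by the algebra of what each candidate comparison estimates.

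**1. Which tests form the pair?**

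| Source | Before rTMS | After rTMS |
|---|---|---|
| 6.2.2 and 6.2.5, outside the scan | Stroop listed as baseline | No Stroop; HIP only |
| 6.2.2 and 6.2.5, in the scanner | Hypnotic and non-hypnotic runs | Hypnotic and non-hypnotic runs, same order |
| 9.6.2 B | Baseline Stroop | Stroop after the post-rTMS scans |

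The retest in 9.6.2 is not in the 6.2.5 list. The one set of runs that is matched on both sides of rTMS is described only as a measure of brain response.

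**2. What does each comparison estimate?** Let I be interference, N the non-hypnotic condition and H the hypnotic one. Suppose that from before to after rTMS:

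- practice or time changes interference by p_N and p_H, equally in both arms;
- active rTMS has a direct effect d on conflict control in both conditions (Section 9.1 allows either sign);
- a rise in hypnotizability lowers I_H by a further h > 0.

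Active minus sham change is then:

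- ordinary Stroop, no hypnotic instruction: (p_N + d) − p_N = **d**;
- Stroop under hypnotic instruction only: (p_H + d − h) − p_H = **d − h**;
- reduction score R = I_N − I_H: [(p_N + d) − (p_H + d − h)] − [p_N − p_H] = **h**.

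The first does not contain h. The second mixes h with d. Only the third isolates h. If the direct effect differs between conditions (d_N and d_H), the third becomes h + d_N − d_H, so the separation is exact only when the two are equal.

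**3. Direction.** Section 9.6.2 expects the Stroop Effect to increase. In the first comparison that requires d > 0, which is worse conflict control. In the second, a genuine gain with h > d appears as a decrease and counts against the hypothesis. In the third, success is an increase in R, which agrees with Section 1.2.

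**4. Timing.** A test after a one-hour scan falls at least 60 minutes after stimulation. Section 9.6.2, under Hypothesis D, describes "Long-lasting (~1 hour) inhibitory rTMS"; Section 5.1 refers to several hours. On the first figure the retest is at or past the end of the effect, on the second it is well within it. The documents do not settle which applies.

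**The case against.** **The Stroop Effect may be shorthand.** Under Hypothesis D, Section 9.6.2 speaks of a post-hypnotic Stroop Effect that increases with hypnotizability. If Outcome B means the same, the direction agrees with Section 1.2. The text of Outcome B does not say so, and still gives no contrast or score.

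**Ordinary interference may be intended.** Section 9.1 also argues that conflict-task performance correlates with hypnotizability. A pre/post test without suggestion would then address the Sections 3 and 9.1 wording. This stands as a reading, but it makes the direct rTMS effect harder to rule out.

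**Appendix 4 is not in the available text.** Section 5.2 places the Hypnotic Stroop procedures there, and instructions and scoring may be given in it. That limits the claim to what the protocol body and SAP state. It does not remove the conflict among Sections 6.2.2, 6.2.5 and 9.6.2.

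A reader might infer more than the documents support:

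- *That hypnotic Stroop reduction is not measured at all.* The matched in-scanner runs could supply it if responses are recorded. What is missing is their assignment to Outcome B.
- *That the retest is the sixth Stroop run of the day and spoiled by practice.* The number of administrations is never stated. The Section 6.2.2 list is not chronological either: the HIP bullet precedes the scan block, yet its first assessment is timed after the scan. Practice common to both arms cancels in the arm comparison.
- *That late timing dilutes the effect.* This depends on which stated duration is believed.
- *That the post-scan test should be dropped.* Nothing in the text requires that.

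**Conclusion.** The point holds and should be corrected. As written, the Stroop part of Secondary Outcome B has no stated hypnotic contrast, carries two opposing directions, and relies on a retest missing from the list of post-rTMS evaluations. Neither a positive nor a null result could be read as evidence on hypnotizability.

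The size is qualitative. It affects one of three measures in a secondary outcome, and Section 9.7 puts the emphasis for secondary aims on magnitude. That emphasis does not help here, because an effect size on an undefined score is no easier to interpret than a p-value. The primary connectivity outcome and the HIP analysis in the SAP are not touched.

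The conclusion rests on two assumptions: that the Section 1.2 wording is the intended hypothesis, and that Appendix 4 does not already define the contrast. The late timing of the retest is a minor note only.

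**What to change.** 1. In Section 9.6.2 B, define the Stroop outcome as interference in the non-hypnotic run minus interference in the hypnotic run, calculated before and after rTMS, with the change compared between arms. Use the in-scanner runs already planned in matched order, provided behavioural responses were recorded. State the interference score explicitly.
2. State the expected direction as greater reduction with active rTMS, and bring Hypothesis B in Sections 3 and 9.1 and the expectation in 9.6.2 into line with Section 1.2.
3. Report the non-hypnotic run, and the post-scan Stroop if it is kept, separately as measures of ordinary conflict control.
4. Reconcile Sections 6.2.2, 6.2.5 and 9.6.2, and Table 2, on which Stroop tests are given and when.
5. The SAP speaks of data collection as finished and does not cover Stroop. Add the definition there and disclose which Stroop data were used. If it is set after Stroop results by arm have been seen, label it post hoc.

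The cost is mainly wording, with no added testing. The downsides are that the definition depends on saved in-scanner responses, which the available text does not describe, and that the stand-alone pair becomes a supporting measure.
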